12.3 Sample Size and Accrual

The study will enroll 63 eligible patients who receive at least one dose of the study agent.

The sample size of the study is determined by the analysis of iPFS. To detect an improvement of median iPFS = 5.2 months from 4.0 months in historical control (IMpower 133) (HR = 0.77) using a logrank test, 60 treated patients will be required to achieve approximately 81% power at a one-sided significance level of 0.15. Patients are accrued for a period of 22 months. Follow-up continues for 12 months after the last patient is enrolled. The probability that a patient experiences an event during the study is 0.9707. The expected number of events during the study is 58. It is assumed that the survival time is exponentially distributed. The sample size calculation above is conducted in PASS v16.0.2. Assuming a 5% rate of dropout prior to protocol treatment, a total of 63 eligible patients will be treated by at least one doses of the study agent.

The sample size calculation is determined to have adequate power to reject the null hypothesis when the alternative hypothesis is true for the primary endpoint iPFS. Whether it has sufficient power for addressing secondary endpoints or exploratory analysis is not of concern.

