Platinum and etoposide typically results in a very high initial response rate (~60-80%) and modest progression free survival (~4-6 months), with median overall survival of less than twelve months in the majority of patients [5-7]. Despite initial chemosensitivity, a hallmark of SCLC is the development recalcitrant behavior to subsequent lines of chemotherapy resulting in dismal outcomes in the refractory setting. Prophylactic cranial irradiation (PCI) has been studied and utilized extensively over the past several decades to improve outcomes by treating occult micrometastatic disease and reducing the incidence of brain metastases. A meta analysis of PCI in the limited stage setting, in SCLC demonstrated a marked reduction in brain metastases from 59% to 33% and improved 3 year survival from 15.3 to 20.7 months [8]. However, in ES SCLC, data regarding the role of PCI has been conflicting. The initial phase III EORTC study of 286 patients randomized PCI or observation following initial 4-6 cycles of chemotherapy [9]. While the incidence of symptomatic brain metastases and survival improved in the PCI arm, the results were criticized as MRI was not routinely performed prior to PCI and therefore likely included a portion of patients with brain metastases. In a separate study from Japan, 224 patients with response to chemotherapy were randomized to receive either PCI or observation [10]. All patients had a baseline MRI prior to enrollment and every 3 months during follow up. The study was stopped early due to futility and a trend was noted with worse survival in patient receiving PCI compared with observation.

In March 2019, the anti-PD-L1 antibody atezolizumab combined with carboplatin and etoposide, a topoisomerase II inhibitor, was FDA-approved for first-line treatment of ES SCLC [11]. This priority approval was based on the results of the IMpower133 study (NCT02763579), a trial which allowed but was not specifically designed for patients with brain metastases. As a result, of the 403 patients, only 35 (9%) had brain metastases. Additionally, recent results from the CASPIAN study of chemotherapy with or without durvalumab included approximately 10% of patients with brain metastases [12]. Thus, limited data exists currently regarding clinical outcomes of patients with SCLC and brain metastases at time of diagnosis.

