Given the recent approval of atezolizumab, the current first-line systemic treatment approach for patients with ES SCLC is a combination of anti-PD-L1 antibody with a chemotherapy regimen of platinum plus etoposide, based on the IMpower133 study (NCT02763579) [18]. The addition of atezolizumab, an anti-PD-L1 antibody, to carboplatin and etoposide for first-line treatment of ES SCLC improved overall (OS) to 12.3 months, from 10.3 months with placebo, and progression-free survival (PFS) to 5.2 months (versus 4.3 months for placebo). While this study allowed ES SCLC patients with brain metastases, only 35 patients (n=17-18 per arm, 9%) had brain metastases; the study was unpowered to assess efficacy in this patient population [18].

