1.4 Rationale

The IMpower133 clinical trial evaluated chemotherapy and atezolizumab for first line treatment of patients with untreated ES SCLC. The results from the trial led to an FDA approval and established this regimen as a new standard of care. However, while patients with brain metastases were allowed, prior cranial radiation was required for these patients. Furthermore, only 9% of enrolled patients had brain metastases. There remains an urgent need to define clinical outcomes for patients treated with chemotherapy and atezolizumab with asymptomatic, untreated brain metastases.

Recent studies with systemic immunotherapy in brain metastases patients have demonstrated that outcomes for patients with and without brain metastases are generally similar. The IMpower133 study demonstrated PFS outcomes of 5.2 months for the atezolizumab arm versus 4.3 months for the placebo arm. Thus, we hypothesize that atezolizumab plus chemotherapy (i.e. carboplatin and etoposide) will improve intracranial progression free survival (iPFS) in patients with brain metastases from SCLC relative to historical controls (\geq 5.2 months vs. 4 months).

This study will enroll patients with asymptomatic brain metastases and untreated ES SCLC. Patients will be treated with combination carboplatin, etoposide, and atezolizumab. Restaging radiographic imaging will occur every 6 weeks (approximately every 2 cycles of treatment). At time of progression, patients can pursue standard of care treatment and radiation therapy off study. Our hypothesis is that the addition of atezolizumab will improve intracranial progression free survival in patients with untreated brain metastases. Furthermore, the study will provide valuable insight in the clinical outcomes of the patient population with ES SCLC and brain metastases. In general, chemotherapy response rates are expected to be high, and immune checkpoint therapy is known to have efficacy in other CNS malignancies. We believe treatment with systemic therapy alone will 1) delay time to WBRT 2) preserve quality of life longer 3) allow a subpopulation of patients to avoid WBRT and 4) be able to avoid a detrimental impact on survival given the close radiographic follow up.

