3. ELIGIBILITY CRITERIA

3.1 Inclusion Criteria

Subject must meet all of the following applicable inclusion criteria to participate in this study:

1. Written informed consent and HIPAA authorization for release of personal health information prior to registration. **NOTE:** HIPAA authorization may be included in the informed consent or obtained separately.
2. Age \geq 18 years with ability and willingness to provide informed consent.
3. ECOG Performance Status of 0-2.
4. Histological confirmation of Small Cell Lung Cancer- Extensive Stage (SCLC) per Veterans Administration Lung Study Group (VALG).
5. At least one untreated asymptomatic brain metastasis that is measurable by RECIST 1.1 that has not been previously irradiated.
6. No prior treatment for metastatic disease. **EXCEPTION:** A single cycle of chemotherapy (platinum/etoposide) with or without atezolizumab is allowed within 30 days prior to enrollment.
7. Treatment-free for at least 6 months since last chemo/radiotherapy, among those treated (with curative intent) with prior chemo/radiotherapy for limited-stage SCLC.
8. Any prior cancer treatment must be completed at least 6 months prior to registration and the subject must have recovered from all reversible acute toxic effects of the regimen (other than alopecia) to Grade \leq 1 or baseline. **NOTE:** a single cycle of chemotherapy (platinum/etoposide) with or without atezolizumab is allowed within 30 days prior to enrollment. **NOTE: Extracranial radiation is allowed.**
9. A concurrent diagnosis of a separate malignancy is allowed if clinically stable and does not require tumor-directed therapy.

10. Demonstrate adequate organ function as defined in the table below

System	Laboratory Value
Hematological	
Absolute Neutrophil Count (ANC)	2 1.5K/mm ³ without GCSF
Hemoglobin (Hgb)	2 9 g/dL (without transfusion)
Lymphocyte Count	2 500/ μ L
Platelet Count	2 100,000/ μ L without transfusion
Renal	
Calculated creatinine clearance	2 50 cc/min
OR	
Serum Cr	< 1.5 x institutional ULN
Hepatic	
Bilirubin	< 1.5 \times upper limit of normal (ULN)
Aspartate aminotransferase (AST)	< 2 \times ULN without liver metastasis < 5 \times ULN with liver metastasis
Alanine aminotransferase (ALT)	< 2 \times ULN without liver metastasis < 5 \times ULN with liver metastasis

¹ Cockcroft-Gault formula will be used to calculate creatinine clearance

² Patients with known Gilbert disease who have serum bilirubin level < 3x ULN may be enrolled

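### Section 12.3 credits its 4.0-month iPFS null to IMpower133, but the only control median the protocol reports for that trial is 4.3 months of overall PFS

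*Combined protocol and SAP*

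**What the plan says.** Section 12.3 (Sample Size and Accrual) sets the comparison: "To detect an improvement of median iPFS = 5.2 months from 4.0 months in historical control (IMpower 133". It adds a hazard ratio of 0.77, a log-rank test, 60 treated patients, about 81% power at one-sided 0.15, 22 months of accrual, 12 months of further follow-up, exponential times and 58 expected events.

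IMpower133's results are reported twice, both times as PFS without an intracranial restriction. Section 1.2 has "progression-free survival (PFS) to 5.2 months (versus 4.3 months for placebo" and section 1.4 has "PFS outcomes of 5.2 months for the atezolizumab arm versus 4.3 months for the placebo arm". On population, section 1.2 says "only 35 patients (n=17-18 per arm, 9%) had brain metastases" and section 1.4 says "prior cranial radiation was required for these patients". This trial's inclusion criterion 5 instead asks for "At least one untreated asymptomatic brain metastasis that is measurable by RECIST 1.1 that has not been previously irradiated".

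Section 1.4 then states the iPFS hypothesis against unnamed historical controls as "5.2 months vs. 4 months". It presents this as following from the IMpower133 figures and from a general premise that, under systemic immunotherapy, patients with and without brain metastases fare similarly. Section 1.1 gives platinum-etoposide a "modest progression free survival (~4-6 months" range, tied neither to IMpower133 nor to iPFS.

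The primary objective (2.1.1) is to estimate iPFS. Section 12.6.1 plans a Kaplan-Meier median with 95% CI and contains no hypothesis test. Section 12.7 has a futility log-rank test but names no null for it.

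**The concern.** In a single-arm trial the fixed null stands in for the control group. Here it carries the stated power, and 12.3 describes beating it as improving on the control of a named trial. A reader who looks up that control in the same protocol finds a different number for a different endpoint, in patients whose brain metastases had been irradiated. Nothing in the documents gets from one to the other. What is at stake is how a positive result is described: a trial could reject 4.0 months, be reported as improving on IMpower133, and not have excluded the value the protocol itself reports for that control.

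**Working it through.** **1. The figures side by side**

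| Place | Months | Endpoint | Stated source |
|---|---|---|---|
| 12.3 | 4.0 | iPFS | IMpower133 |
| 1.2 and 1.4 | 4.3 | overall PFS | IMpower133 placebo arm |
| 1.4, hypothesis | 4 | iPFS | unnamed historical controls |
| 1.1 | about 4-6 | PFS | platinum-etoposide in general |

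No IMpower133 iPFS result appears anywhere. The 5.2-month alternative equals that trial's atezolizumab-arm PFS; the 4.0-month null does not equal its control.

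**2. Is 4.0 a misprint for 4.3?** 4.0/5.2 = 0.769, which rounds to the stated 0.77. 4.3/5.2 = 0.827. So 4.0 is the value actually used.

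**3. Events.** For exponential times with λ = ln 2/5.2 = 0.1333, accrual A = 22 and follow-up F, P(event) = 1 − [exp(−λF) − exp(−λ(A+F))]/(λA).
- F = 12: 0.9348, and 60 × 0.9348 = 56.1 events.
- F = 18: 0.9707, and 60 × 0.9707 = 58.2 events.

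The stated 58 events match 18 months rather than the stated 12. That is a separate matter, so both counts are carried below.

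**4. Power, normal approximation.** The log-rank test is read as one-sample, because there is one arm (a two-arm formula with 58 events gives only 48.5%). Power = Φ(√d × ln(m1/m0) − 1.036), with m1 = 5.2.
- m0 = 4.0, ln(1.3) = 0.2624. d = 56.1: Φ(1.965 − 1.036) = 0.823. d = 58: Φ(1.998 − 1.036) = 0.832.
- m0 = 4.3, ln(5.2/4.3) = 0.1900. d = 56.1: Φ(1.423 − 1.036) = 0.651. d = 58: Φ(1.447 − 1.036) = 0.659.

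**5. Power, simulating the test itself.** n = 60, one-sided 0.15, no futility rule, no dropout, 100,000 to 200,000 trials per setting. The statistic is (E − O)/√V, where V is E or (O + E)/2; ranges cover both.

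| Null median | True 5.2, F = 12 | True 5.2, F = 18 |
|---|---|---|
| 4.0 | 0.814-0.823 | 0.820-0.828 |
| 4.1 | 0.762-0.772 | not run |
| 4.2 | 0.703-0.714 | not run |
| 4.3 | 0.638-0.650 | 0.646-0.658 |

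The stated 81% is reproduced at 4.0. At 4.3 the figure is about 65%.

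**6. What rejecting 4.0 excludes.** E grows as the null median falls, so any trial that rejects 4.3 also rejects 4.0. At a true 5.2 (F = 12), trials rejecting 4.0 but not 4.3 are 0.814 − 0.638 = 0.176, or 0.823 − 0.650 = 0.173. As a share of all rejections of 4.0 that is 0.176/0.814 = 0.22, or 0.173/0.823 = 0.21. If the true median were 4.3, the test would reject 4.0 about 30-31% of the time. If it were 3.7 (an assumed value), about 4-5%.

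**The case against.** The strongest reply is that 4.3 and 4.0 belong to different endpoints, so they cannot contradict each other. That stands: the stated source fails to support 4.0, but it does not refute it. The figure could come from an unreported IMpower133 result or from another study with the citation misplaced.

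It can also be said that section 1.4 does connect the two, by drawing its hypothesis from the IMpower133 figures and a premise of similar outcomes with and without brain metastases. That stands in part. The premise is a reason for carrying overall PFS into this population. It does not explain why 4.3 becomes 4, why overall PFS becomes iPFS, or why patients who needed prior cranial radiation can stand for unirradiated ones. Rounding is possible but not stated.

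Third, the harm is limited. The objective is estimation, and the planned median and CI can be read against either value. Under the plan's exponential assumption, an observed 5.2 with 58 events gives 5.2 × exp(±1.96/√58), or 4.0 to 6.7, which visibly includes 4.3. This also stands, and it is why no extra test is needed.

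A reader might infer more from the numbers than they carry:
- *The trial is underpowered.* Keeping 81% power against 4.3 would take about 109-116 patients, but the documents do not show 4.3 to be the right iPFS null.
- *Type I error is 30% instead of 15%.* The 30% is power at a value above the null, not type I error.
- *The benchmark is too lenient.* The direction is unknown. Counting only intracranial progression and death would tend to lengthen the median, and unirradiated brain disease could shorten it.
- *The futility look shares the fault.* Section 12.7 names no null, so this is inference.

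**Conclusion.** The concern holds as a gap in source and justification. The 4.0-month null is not supported by the trial 12.3 cites for it, and no passage derives it as an iPFS benchmark for unirradiated brain metastases. The stated power is right for 4.0. Measured against the only IMpower133 control value in the documents, the same 60 patients give about 65%, so a rejection of 4.0 should not be described as improvement over that control. The 4.3 figure serves only as a sensitivity value. The results assume a one-sample log-rank test, exponential times, uniform accrual, one-sided 0.15, 56 to 58 events and no futility rule; changing follow-up from 12 to 18 months moves them by less than one percentage point. The point merits correction, but it does not call for a redesign.

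**What to change.** In 12.3 and 1.4, do one of two things:
- replace the IMpower133 label with the actual source of 4.0 months, and justify that value as an iPFS benchmark for unirradiated brain metastases; or
- explain how 4.0 is obtained from IMpower133, given the reported 4.3.

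In either case add to 12.3:

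> Power is about 81% against 4.0 months and about 65% against 4.3 months, the overall-PFS control median reported for IMpower133 (one-sample log-rank, n = 60, one-sided 0.15, 56-58 events, no futility rule); rejecting 4.0 months does not by itself show improvement over the IMpower133 control.

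Section 12.6.1 can stay as it is. The null, sample size, alpha and tests do not change, and no patients or data are added. The cost is a few sentences and a less favourable power figure printed beside the stated one.

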OBJECTIVES	
Primary Objective
 
1.) Intracranial progression free survival (iPFS)
 
Secondary Objectives
 
1.) Overall response rate (ORR) 2.) Extracranial Progression free survival (PFS) 3.) Overall survival (OS) 4.) Toxicity of atezolizumab plus carboplatin and etoposide
 
Exploratory Objectives
 
1.) Explore circulating biomarkers in patients with SCLC brain metastases 2.) Explore patient-reported quality of life (QoL) 3.) Investigate the immune and genomic landscape of SCLC primaries that metastasized to the brain

STUDY DESIGN	Single arm, multicenter phase II trial for n=60 patients with untreated extensive stage (ES) small cell lung cancer (SCLC) and asymptomatic brain metastases.
KEY ELIGIBILITY CRITERIA (See Section 3 for full eligibility criteria)	
 • Histological confirmation of Small Cell Lung Cancer- Stage IV/Extensive Stage (SCLC) per Veterans Administration Lung Study Group (VALG). • Untreated, asymptomatic brain metastases • No prior systemic therapy for metastatic disease [a single cycle of chemotherapy (platinum/etoposide) with or without atezolizumab is allowed within 30 days prior to enrollment]
STATISTICAL CONSIDERATIONS	A Kaplan-Meier curve will graphically describe iPFS, PFS, and OS among patients treated by at least one cycle of Atezolizumab. Median survival, as well as 6-month iPFS and PFS, and 12-month OS will be estimated with their 95% confidence intervals (CI). The impact of patients' demographics and baseline clinical characteristics on survivals will be evaluated in the context of a Cox PH model. The ORR, the proportion of treated subjects with a complete or partial response, will be calculated with its 95% CI. The

	
association of ORR with patients' demographics and baseline clinical characteristics will be evaluated in a logistic regression model.
 
The quality of life of treated patients at baseline and during treatment will be summarized and the patients' demographics and baseline clinical characteristics on the change of the quality of life will be evaluated in a linear regression.

TOTAL NUMBER OF SUBJECTS	N = 63 eligible patients (60 evaluable)
ESTIMATED ENROLLMENT PERIOD	Estimated 22 months from lead site opening to accrual
ESTIMATED STUDY DURATION	Estimated 40 months

TABLE OF CONTENTS

Schema	6
1. Background and Rationale	7
2. Study Objectives and Endpoints	10
3. Eligibility Criteria	11
4. Subject Registration	15
5. Treatment Plan	15

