- 7: Archival tissue is required if available. Archival tissue should be identified and requested at screening and shipped by Cycle 2 Day 1, if available. If archival tissue is not available, the subject may still be eligible for the trial. See CLM for collection, labeling, and shipping instructions. Subjects will also be consented for optional storage of any remaining tissue samples after protocol-specified studies are complete. These samples will be stored for future unspecified cancer-related research and are considered “banking samples”.

8: Blood (whole blood for PBMCs, plasma and buffy coat for germline DNA) for correlative analysis will be drawn prior to treatment on Cycle 1 Day1, Cycle 3 Day 1 and at the D30 safety visit/progression. Additional details regarding correlatives can be found in Section 8 and the CLM.

9: If screening (baseline) CBC and Chemistry (CMP) were performed within 7 days of Day 1 of treatment, these do not need to be repeated. All laboratory assessments should be done prior to treatment.

10: Safety Follow Up: The safety follow-up visit should only occur when subjects permanently stop study treatment for whatever reasons (toxicity, progression, or other reason) and should be performed 30 days (+ 7 days) after the last dose of treatment. Subjects who have an ongoing Grade ≥ 2 or serious AE (SAE) at this visit will continue to be monitored by a member of the study team until the event is resolved, stabilized, determined to be irreversible by the site investigator or a new anti-cancer treatment starts, whichever occurs earlier.

11: Long Term Follow Up: For subjects who discontinue for reasons other than progressive disease, radiographic disease assessment should be performed every 9 weeks until progression, initiating a new cancer treatment, withdrawing consent or becoming lost to follow-up. The scan interval may be reset if scans were done sooner for clinical reasons and the type of scan may be left to discretion of the site investigator. This imaging may be done locally. Once disease progression is documented, subjects will be followed for survival every 3 months for 1 year from documented progression. Follow up may be accomplished via clinic visit, phone call, or other avenues as appropriate. A window of ± 14 days will be applied to follow up.

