12.7 Interim Analysis/Criteria for Stopping Study

One interim analysis for futility will be conducted at half of the required events for the final analysis (approximately 29 events) based on the Wieand rule [30]. If the one-sided p-value of the logrank test exceeds 0.50, the trial will be terminated for futility, declaring the probability of rejecting the null hypothesis is very low. The Wieand rule to futility monitoring negligibly reduces the power of the trial, usually less than 2% and offers a 50% chance of early stopping accrual to an ineffective therapy.

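### The event probability and 58 events in 12.3 fit 18 months' follow-up, not the 12 months stated, and the futility look costs more power than 12.7 suggests

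*Combined protocol and SAP*

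**What the plan says.** Section 12.3 tests a 5.2-month median iPFS against 4.0 months with a log-rank test at one-sided 0.15. It requires 60 treated patients for about 81% power, with exponential survival and 22 months of accrual. On timing it says "Follow-up continues for 12 months after the last patient is enrolled". It then gives two results: "The probability that a patient experiences an event during the study is 0.9707" and "The expected number of events during the study is 58". It does not mention an interim look.

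Section 12.7 adds one futility analysis, which "will be conducted at half of the required events for the final analysis (approximately 29 events"). The trial stops if the one-sided p-value exceeds 0.50. On the cost it says only: "The Wieand rule to futility monitoring negligibly reduces the power of the trial, usually less than 2" per cent.

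The synopsis gives the enrolment period as "Estimated 22 months from lead site opening to accrual" and the study duration as "Estimated 40 months". Footnote 11 of the study calendar adds survival follow-up: "Once disease progression is documented, subjects will be followed for survival every 3 months for 1 year from documented progression".

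**The concern.** There are two problems.

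- **Follow-up and event count do not match.** The accrual, follow-up and median in 12.3 determine the event probability once an accrual pattern is assumed. The printed value is too high for 12 months. Section 12.7 treats the resulting 58 as the number of events required and derives the interim trigger from it. A team following the text cannot tell whether the iPFS cut-off is month 34 or the later date at which 58 events are expected. In an open-label single-arm trial that choice should not be left until data have accrued.
- **The quoted power omits the look.** The plan's only statement of the cost is a general remark about the rule. A stop at p > 0.50 is cheap when the final alpha is small. It is dearer at 0.15, because many trials that would have ended just past a lenient final boundary are below zero at the halfway point.

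**Working it through.** **Inputs.** From 12.3: medians 5.2 and 4.0 months, accrual A = 22, follow-up F = 12, N = 60, one-sided alpha 0.15, exponential survival. From 12.7: look at about 29 events, stop if p > 0.50. Uniform accrual is my assumption, because the documents give no pattern.

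**Step 1: reproduce the printed probability.** With λ = ln 2 / median,

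p = 1 − [exp(−λF) − exp(−λ(A+F))] / (λA).

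For median 5.2, λ = 0.1333 and λA = 2.9325.

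- F = 12: p = 1 − (0.20198 − 0.01076)/2.9325 = 0.9348, and 60 × 0.9348 = 56.1 events.
- F = 18: p = 1 − (0.09078 − 0.00483)/2.9325 = 0.9707, and 60 × 0.9707 = 58.2 events.

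Solving p = 0.9707 for F gives 18.00 months. The synopsis duration of 40 months equals 22 + 18, whereas 12.3 as worded implies 22 + 12 = 34.

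**Step 2: can another reading rescue 12 months?**

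| Variant at F = 12 | Event probability | Events of 60 |
|---|---|---|
| Median 4.0 (null) | 0.9679 | 58.1 |
| Median 4.6 (midpoint) | 0.9523 | 57.1 |
| Median 5.2, accrual rate rising linearly from zero | 0.9067 | 54.4 |
| Median 5.2, accrual rate falling linearly to zero | 0.9629 | 57.8 |

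None reaches 0.9707. An exponentially declining accrual rate does, but only with about 86% of patients enrolled in the first 11 months. The null median comes closest and would round to 58 events, but its probability is not the printed one.

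**Step 3: chance of reaching 58 events.** Binomial with 60 patients and true median 5.2: P(at least 58) = 0.24 at F = 12 and 0.74 at F = 18.

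**Step 4: power without the look.** A one-sample log-rank variance formula gives 80.3% at 12 months and 80.8% at 18. The normal approximation Φ(√d · ln 1.3 − z), where d is the expected number of events and z = 1.036, gives 82.3% at d = 56.1 and 83.3% at d = 58.2. Simulation gives 81.6–83.2% and 82.0–83.6%, depending on the variance form. So 81% is a fair fixed-sample figure at either follow-up.

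**Step 5: power with the look.** Normal approximation: bivariate normal with drift √d · ln 1.3 and correlation equal to the square root of the information fraction, requiring Z > 0 at the look and Z > 1.036 at the end. Simulation: 200,000 one-sample log-rank trials per case, using expected, averaged or observed events as the variance.

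| Case | Normal: without → with (loss) | Simulation: with look (loss) |
|---|---|---|
| F = 12, look at 28 | 82.3 → 79.8 (2.6) | 78.0–79.3 (3.7–4.0) |
| F = 18, look at 29 | 83.3 → 80.7 (2.6) | 78.4–79.7 (3.6–3.9) |
| As printed: F = 12, look at 29 | 82.3 → 80.0 (2.3) | loss 3.4–3.7 |

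Power is in per cent and losses are in points. Starting from exactly 81%, the normal approximation with a look at half the information gives 78.4%, a loss of 2.6 points. In simulation, about 10% of trials stop when the true median is 5.2.

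**Step 6: why the general remark fails here.** By the same normal approximation from 80% power, the rule costs 0.3 points at one-sided alpha 0.025 and 0.7 at 0.05. The 2.6 points at 0.15 come from the lenient alpha.

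**The case against.** The best case for leaving the text alone runs as follows.

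- **The mismatch hardly affects power.** True. Fixed-sample power moves by 1 point or less, and 56 and 58 events are close. This is probably one wrong number in one sentence.
- **58 is an expectation, not a target.** Section 12.3 does call it expected and gives a calendar cut-off, and no section makes the final analysis wait for 58 events. But 12.7 calls the same number required and uses it to set the interim.
- **63 patients are to be treated.** With 63, 12 months gives 63 × 0.9348 = 58.9 events and a 77% chance of at least 58. That weakens the 24% figure, which depends on 60. It does not explain 0.9707, which is a per-patient probability and does not change with N. The power calculation also rests on 60.
- **The 2% remark is general.** That is so. It does not apply to this design, rather than being a false design figure. It is still the only cost the plan gives, and it is described as negligible.
- **The excess over 2 points depends on method.** For the printed combination the normal approximation gives 2.3 points, and a look at 55% of the information would give 1.9. Simulation of the log-rank test gives at least 3.4 for the printed combination.

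These points limit the seriousness of the finding. None of them makes 12 months and 0.9707 compatible.

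**Conclusion.** The concern holds. As worded, 12.3 combines 12 months' follow-up with an event probability and event count that belong to 18 months. The differences are 0.935 against 0.9707, 56 against 58 events, and month 34 against month 40. This rests on exponential survival, which 12.3 states, and on uniform accrual, which it does not. Only strongly front-loaded accrual would reach 0.9707 at 12 months.

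The 81% is power without the futility look. With the look at half the events, the loss is about 2.5 to 4 points (2.3 at the lowest, for the printed combination by normal approximation). Power is then about 78–80% by simulation and 79.8–80.7% by normal approximation. The exact value depends on the variance form of the one-sample log-rank test, which the plan does not give.

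Neither point undermines the sample size or the decision rule. They should be corrected because the cut-off, interim trigger and quoted power currently describe more than one design.

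**What to change.** 1. In 12.3, state one consistent set and the accrual assumption: either 18 months' follow-up, 0.9707, 58 events and an interim at about 29, or 12 months, 0.935, 56 events and an interim at about 28. Make 12.7 match.
2. Reconcile the synopsis duration of 40 months with that choice and with the one-year survival follow-up after progression in the study calendar.
3. In 12.3 and 12.7, label 81% as power without the interim look. State the variance form of the one-sample log-rank test and the power with the look computed for that form, expected to be about 78–80%. Replace the general remark on cost with the loss for this design, about 2.5 to 4 points.
4. While editing, list the one-sample log-rank test against the 4.0-month null in 12.6.1, beside the Kaplan-Meier estimates. This is tidying, since 12.3 already defines the test.

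The cost is wording only: no added patients and no change to the stopping or final decision rule. The quoted power with the look may read up to about 3 points below 81%. Choosing 18 months puts the iPFS cut-off 6 months later than choosing 12.
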